### **Inclusion Criteria**

Patients seen the emergency department (ED) will be enrolled in this study if they 1) are aged 18-55, 2) have suffered a TBI with documented evidence of loss of consciousness (LOC) which was less than 24 hours, 3) were injured between 3 months and 15 years ago, 4) received a Glasgow coma scale (GCS) score of between 9 and 15 upon ED admission, 5) experienced less than 1 week of post-traumatic amnesia (PTA), and 6) have post-traumatic cognitive symptoms as evidenced by endorsing at least 1 out of 4 cognitive symptoms on the Neurobehavioral Symptom Inventory (NSI), a measure of post-traumatic symptoms from the NIH Common Data Elements, and 7) have been on stable doses of any psychotropic medications for the past 2 months.. Healthy controls will be between the ages of 18-55.

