### **Exclusion Criteria**

Potential participants will be excluded from participation in this study if there is 1) a prior history of other neurological disease or any history of seizures, 2) history of psychosis 3) history of current or recent (within two years) substance/alcohol dependence, 4) any discontinuity in skull electrical conductivity (i.e., unhealed burr holes in scalp) or artificially constructed (metal or plastic) craniotomy cover; 5) presence of any implanted electrical device (e.g. pacemaker), 6) recent medical instability (within three weeks), 7) any condition that would prevent the subject from completing the protocol, 8) appointment of a legal representative, as assessed via direct inquiry of the subject and a designated trusted other. Because our population will have only mild to moderate TBIs, and be well beyond the subacute phase of injury (> 3 months), ongoing complications from the injury itself such as skin infection, bleeding, ischemia, swelling, increased intracranial pressure, seizures, and hyponatremia will be extremely unlikely. However, these would be considered exclusionary criteria if present over the previous three weeks prior to enrollment. Adults unable to consent, individuals who are not yet adults (infants, children, teenagers), pregnant women, and prisoners are specifically excluded from the study. Persons not fluent in English will be excluded, as the neuropsychological test batteries are administered in English.

PROTOCOL TITLE: Transcranial direct current stimulation for treatment of deficits after traumatic brain injury.

TARGETED/PLANNED ENROLLMENT: Number of Subjects			
Ethnic Category	Sex/Gender		
	Females	Males	Total
Hispanic or Latino	26	38	64
Not Hispanic or Latino	38	58	96
Ethnic Category: Total of All Subjects *	64	96	160
Racial Categories			
American Indian/Alaska Native	4	4	8
Asian	2	2	4
Pacific Islander	2	2	4
Black or African American	2	2	4
White	46	66	112
Other races	10	16	26
Two or more races	2	4	6
Racial Categories: Total of All Subjects *	64	96	160

PROTOCOL TITLE: Transcranial direct current stimulation for treatment of deficits after traumatic brain injury.

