below the deltoid. Current for the treatment condition will be applied at 2.0 mA for a total delivered charge of 60 mA-min.

*Safety of stimulation.* During tDCS application, subjects will describe physical sensations such as tingling or itching using a 10-point anchored Likert scale. Administration of tDCS will be stopped immediately if subjects report a 7 or above for discomfort, or if subjects wish to stop at any time. Subjects will also have their mood, energy, pain, and arousal levels assessed using visual analog 10-point scales. These checks will occur every ten minutes during the stimulation session.

*Double blind design and sham treatment:* The sham stimulation (control) group will receive up to 0.2 mA current for 30 minutes each session, with an initial ramping up and down of stimulation to mimic active stimulation. The sham current is used as a control condition, rather than the absence of stimulation, to equate aspects of the procedure (preparation and application of electrodes, attachment with adhesive strips, etc.), and to give the participant a degree of physical sensation that is somewhat similar to that of the 2.0 mA stimulation group while remaining well below the level sufficient to affect brain function and behavior. To accomplish a double blind, the tDCS machine is programmed to randomize sham versus active stimulation and keeps track of the stimulation protocol for later downloading.

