### Experimental Design and Methods

**Recruitment:** Recruitment, enrollment, and data collection for Aim 2 will be identical to the experimental design of Aim 1. Subjects will be randomly assigned to active stimulation or sham stimulation groups.

**Depression Assessments:** As part of the neuropsychological test battery administered to the participants before, immediately after, and at 1 month after tDCS, subjects will be assessed for depressive symptoms using NIH Common Data Elements instruments as well as reliable and valid instruments for detecting mood disturbances in TBI populations. These tests are the Beck Depression Inventory (BDI-II), and the Hamilton Rating Scale for Depression (HAM-D). Post-traumatic stress disorder (PTSD) symptoms, which often predispose to depression after TBI, will be assessed using the PTSD Checklist (PCL). These will be conducted verbally, so as to ensure similarity of delivery with the long-term assessments. Any patient who reports thoughts of death or suicidal ideation at any point during the stimulation protocol or assessments will be immediately evaluated by the PI and given appropriate emergency medical care at the UNM Psychiatric Emergency Service.

**Stimulation Protocol:** The protocol will be identical to the stimulation regimen described in Aim 1. During the procedure for each stimulation session, participants will be asked to rate their mood according to a 10-point visual analog scale before and after each stimulation session (10 sessions total). This will monitor for daily fluctuations in mood as well as any rare stimulation-related severe mood changes.

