
## 12. Provisions to Monitor the Data to Ensure the Safety of Subjects

Data safety and monitoring will be carried out to ensure and maintain the scientific integrity of this project and to protect the safety of our participants. Safety monitoring is the process during the study that involves review of accumulated outcome data for groups of subjects to determine if any of the procedures practiced should be altered or stopped. Ultimately, the PI ([name]) will be responsible for monitoring the safety of the study and complying with the reporting requirements. An independent Data Safety and Monitoring Board (DSMB) will review the study data on a quarterly basis with the PI to ensure participant safety. The DSMB for this study will be composed of [name], the medical director of the Electroconvulsive Therapy Service at UNM, and [name], staff epileptologist of the Epilepsy Monitoring Unit at UNM. Their experience in assuring safety of brain stimulation therapies and seizure monitoring protocols make them ideally suited to serving on this project's DSMB. Continuous, close monitoring of participant safety will include prompt and frequent reporting of safety data (i.e., adverse/serious adverse events) to the

**PROTOCOL TITLE:** Transcranial direct current stimulation for treatment of deficits after traumatic brain injury.

DMSB, the University of New Mexico Health Sciences Center Institutional Review Board (UNMHSC IRB) and/or appropriate NIH staff with oversight responsibility. The PI will provide a summary of the safe conduct of the study to NIH on an annual basis as part of the progress report. All AEs occurring during the course of the study will be collected, documented, and reported to the UNMHSC IRB.

The review of data may result in early termination of the study, amendment to the protocol, or changes to the data collection plan or study forms if it appears that there are adverse events occurring at a rate significantly greater than that found in similar tDCS studies involving subjects with neurological disorders (ie. stroke). Should the protocol or data collection plans or study forms be amended as a result of data review, the IRB will be notified and the amendment approved prior to study amendment implementation. In addition, the participants will be notified of any significant new findings that develop during the course of research that may affect their wish to continue participation in the study.

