Rare mood changes with tDCS have been observed in studies of depressed patients, resulting in several cases of hypomania. Most of these patients were taking concurrent antidepressants. Precautions taken in this study include excluding patients on psychotropic medications, and monitoring mood with visual analog scales during stimulation, and pre/post-treatment depressive symptom questionnaires. There has not been a reported instance of suicidality caused by tDCS.

In healthy controls there have been no reported adverse events of TDCS, other than the physical sensations and skin irritation above. Of critical importance is the safety of tDCS in patients with neurological illnesses that may carry some increased vulnerability to either brain damage or seizures. The experimental threshold at which tDCS causes brain injury was found to be two orders of magnitude above the current densities used in humans, making stimulation at the scalp with

**PROTOCOL TITLE:** Transcranial direct current stimulation for treatment of deficits after traumatic brain injury.

contemporary protocols causing brain damage extremely unlikely. tDCS is widely used in post-stroke patients in protocols that place the stimulating electrodes ipsilateral to the lesion and very often close to perilesional areas, without any increased side effects or adverse consequences. Even more reassuring, tDCS at 1.0-2.0 mA has been performed over damaged left frontal cortex in 37 patients with moderate to severe TBIs, who are at the highest risk of post-traumatic seizures and demonstrate the greatest levels of structural damage, without adverse events, seizures, or decrements in neurologic status. A review of and contact with studies registered in clinicaltrials.gov for tDCS in TBI (Spaulding, NYU, U. Leige) did not discover any occurrence of seizures or adverse events.

Safeguard exclusions that the study will have in place are enumerated above, and will ensure that neurologically unstable patients are screened out of the study, or those who might be at higher risk from cranial electrical stimulation. A Data Safety and Monitoring Board composed of [name] and [name], specialists in neurostimulation and seizures respectively, will be meeting with the PI quarterly to review outcome data to ensure rigorous protection of patients, as described below.

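### The risk section says people taking psychotropic drugs are kept out as a precaution against hypomania, but the eligibility criteria let them in

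*Combined protocol and SAP*

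**What the plan says.** Section 16 (Risks to Subjects, tDCS) describes rare mood changes in studies of depressed patients, with several cases of hypomania, and adds: "Most of these patients were taking concurrent antidepressants". It then lists the response: "Precautions taken in this study include excluding patients on psychotropic medications, and monitoring mood with visual analog scales during stimulation", together with depressive symptom questionnaires before and after treatment.

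On eligibility, inclusion criterion 7 asks that TBI patients "have been on stable doses of any psychotropic medications for the past 2 months". Healthy controls are given an age range and nothing else. The psychiatric and substance items in the Exclusion Criteria read "2) history of psychosis 3) history of current or recent (within two years) substance/alcohol dependence"; none of the eight numbered items, and nothing in the text after them, concerns medication.

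On monitoring, Section 10 (Safety of stimulation) says "Subjects will also have their mood, energy, pain, and arousal levels assessed using visual analog 10-point scales", every ten minutes, and Section 13 repeats this. Under Specific Aim 2.1, mood is also rated before and after each session: "This will monitor for daily fluctuations in mood as well as any rare stimulation-related severe mood changes". The same aim provides that "Any patient who reports thoughts of death or suicidal ideation at any point during the stimulation protocol or assessments will be immediately evaluated" by the principal investigator. Section 12 adds "Continuous, close monitoring of participant safety will include prompt and frequent reporting of safety data" and a quarterly DSMB review.

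**The concern.** The risk section names an adverse event, says which patients made up most of the reported cases, and says that such patients are excluded. If the eligibility criteria admit them, an ethics board weighing the risk is relying on a preventive step that does not exist, and what remains is detection.

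The group is a foreseeable one in this trial. Aim 2 treats depressive symptoms, and the Background cites major depression in 33% of patients within a year of TBI. Section 10 calls the stimulation regimen similar to that of a trial comparing tDCS with sertraline, and Section 16 cites that same trial in support of its statement on hypomania.

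There is a practical side too. A screener who follows Section 16 would turn away people whom criterion 7 admits.

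**Working it through.** The point is a comparison of texts. The plan states no figure that needs reproducing.

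**Step 1. Can criterion 7 be read as an exclusion?** No. A requirement that doses be stable for 2 months only makes sense if medicated patients may enrol. It screens out recent dose changes and leaves stable users eligible, antidepressant users among them.

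**Step 2. Does another criterion supply the exclusion?** The eight numbered exclusions cover other neurological disease or seizures, psychosis, substance dependence, skull discontinuity, implanted devices, medical instability, inability to complete the protocol, and a legal representative. Taking a stable antidepressant meets none of them. The unnumbered text after them covers complications of the injury, inability to consent, age, pregnancy, prisoners and English fluency. Section 16 itself refers back to the exclusions listed earlier as its safeguards, and that list has no such item. No other section adds one.

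**Step 3. Who is affected?** TBI patients on stable doses are admitted by criterion 7. Healthy controls are assigned to the same active and sham groups (Section 10, Participants), and their only inclusion criterion is age, so neither stable nor changing psychotropic use bars them. Section 16 speaks of patients, so its sentence may be meant for the TBI group alone. Even so, controls can be stimulated while taking these drugs.

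**Step 4. How many?** Section 10 assigns 40 TBI subjects and 40 controls to each arm, so 40 + 40 = 80 people are planned for active stimulation. The documents give no rate of psychotropic use, so the number exposed while medicated lies anywhere from 0 to 80 and cannot be narrowed.

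**Step 5. What do the remaining precautions do?**

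| Observation | Stated action | Where |
|---|---|---|
| Discomfort of 7 or above, or wish to stop | Stop stimulation | Sections 10 and 13 |
| Pain, or lowered arousal | Stop stimulation | Section 13 |
| Suicidal thinking | Immediate evaluation by the principal investigator, emergency care | Section 10, Aim 2.1 |
| Mood ratings, in session and before/after | None stated | Sections 10 and 13 |

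So mood is measured often, and Aim 2.1 says one purpose is to catch severe mood change. No action is written for the event Section 16 names. The planned questionnaires (BDI-II, HAM-D) are depression scales.

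**The case against.** The strongest reply is that the operative rule is clear and the rest of the safety system is sound. Criterion 7 is unambiguous, and the ethics board receives it in the same document as Section 16. Mood is tracked throughout. The principal investigator, who has a neuropsychiatry background, or a technician gives the stimulation. Adverse events are reported promptly, and a DSMB with expertise in brain stimulation and seizures meets quarterly. Section 16 calls these events rare, and it promises mood monitoring, not a mood stop rule.

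Most of that stands. It limits how serious the point is, but it leaves the false sentence in place. A reader of the risk section should not have to find criterion 7 to discover that a listed precaution does not operate. Reporting and quarterly review also do not tell the person running a session what to do about suspected hypomania.

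Four stronger readings are tempting, and the documents do not support them.

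- *Hypomania goes unmonitored.* It does not; the ratings in Sections 10 and 13 are specified.
- *Admitting medicated patients is unsound.* Allowing stable doses is a design choice, and nothing in the plan shows it to be a poor one.
- *Participants were misinformed.* The consent pages are not available, so this cannot be judged.
- *The mood scale needs a numeric stop threshold.* Improved mood is what Aim 2 hypothesises for active stimulation. A threshold could fire on the intended response, more often in the active arm, cutting dose there and hinting at assignment to staff who are meant to be blinded.

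**Conclusion.** The point holds and should be fixed. Section 16 claims a safeguard against hypomania that the eligibility criteria do not contain, for TBI patients on stable doses. Healthy controls have no medication criterion of any kind.

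The consequence is limited to the accuracy of the safety statement and one missing instruction. The primary endpoint, change in EXAMINER scores, and the stated 80% power do not depend on it. A reader might infer that harm is likely; the documents do not support that, since they describe the events as rare and keep mood monitoring, adverse event reporting and DSMB review in place.

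The conclusion rests on reading criterion 7 in its ordinary sense and on the exclusion list being complete as printed. It assumes no rate of psychotropic use.

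**What to change.** 1. In Section 16, replace the claimed exclusion with a statement that participants on stable psychotropic doses may be enrolled and that mood monitoring is the precaution. Restate the hypomania risk on that basis. The sentence must also be true of healthy controls: either say that no medication rule applies to them, or extend criterion 7 to cover them.
2. In Section 10, Aim 2.1, extend the existing rule for evaluation by the principal investigator, now limited to suicidal thinking, to suspected hypomania. Make it a clinical judgement, with stimulation held until the evaluation is done. Do not tie it to a cut-off on the mood scale, for the reason given above.

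The cost is a few sentences of protocol text and an occasional delayed session. No new measurement is needed, and the sample size does not change. Excluding everyone on psychotropic drugs and deleting criterion 7 would also remove the contradiction. That would mean more screening, by an amount the documents do not allow one to estimate, and it is a trade-off for the sponsor, not a necessary correction.

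### The risk section counts exclusion of psychotropic users as a guard against tDCS hypomania, but the eligibility criteria admit them, and no written rule responds to a rise in mood

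*Combined protocol and SAP*

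**What the plan says.** Section 16, under tDCS, reports that rare mood changes, including several cases of hypomania, have been seen in studies of depressed patients. It adds: "Most of these patients were taking concurrent antidepressants". The precautions it then lists are "excluding patients on psychotropic medications, and monitoring mood with visual analog scales during stimulation, and pre/post-treatment depressive symptom questionnaires".

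The Inclusion Criteria set a different rule. Under criterion 7, TBI patients qualify if they "have been on stable doses of any psychotropic medications for the past 2 months". For healthy controls the only stated criterion is age 18 to 55. The Exclusion Criteria open with "a prior history of other neurological disease or any history of seizures, 2) history of psychosis" and go on to substance dependence, skull defects, implanted devices, medical instability and other items. None concerns medication, and neither mania nor bipolar disorder is listed.

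On monitoring, section 10 (Safety of stimulation) says: "Subjects will also have their mood, energy, pain, and arousal levels assessed using visual analog 10-point scales", and "These checks will occur every ten minutes during the stimulation session". Under Specific Aim 2.1 (Stimulation Protocol), mood is also rated before and after every session, with a stated purpose: "This will monitor for daily fluctuations in mood as well as any rare stimulation-related severe mood changes".

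**The concern.** The risk section tells the ethics board and the safety board that the group it links to hypomania will not be enrolled. The criteria enrol that group. Someone who approves the trial on the strength of section 16 would believe in a protection that does not exist.

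The two remaining precautions do not fill the gap. Mood and energy scores are recorded, but the protocol does not say what happens when they climb, which is the direction of the risk that section 16 names. The depression questionnaires are not described as detecting mania. They are given at baseline, after the course and a month later, so they cannot guide a decision between sessions. At stake is whether a patient with emerging hypomania goes on to the next of up to ten weekday sessions. As written, that rests on individual judgement.

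**Working it through.** This is mainly a check of text against text; the plan gives no figure to reproduce.

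**1. One patient, three rules.** Take a TBI patient on an unchanged antidepressant dose for three months.
- Inclusion criterion 7: met.
- Exclusion Criteria: no item applies. Item 7, on conditions that would stop a subject finishing the protocol, does not cover medication use.
- Section 16: excluded.

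The same patient is both eligible and excluded, so the passages cannot both be right.

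**2. Healthy controls.** The two-month rule is written for the TBI patients. Controls are also assigned to active or sham stimulation (section 10, Participants), yet no medication rule is stated for them other than the section 16 sentence.

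**3. Every written action rule, and whether a rise in mood or energy sets it off.**
- Discomfort of 7 or more, or the subject's wish: stop stimulation (sections 10 and 13). No.
- Pain or lowered arousal: stop stimulation (section 13). No; only a fall in arousal counts.
- Suicidal thoughts or thoughts of death: immediate evaluation by the principal investigator (section 10, Depression Assessments). No.
- Adverse events more frequent than in similar tDCS studies: possible amendment or termination (section 12). No; this is an aggregate comparison at quarterly review, whereas the course lasts two working weeks.
- Change of status on a study criterion: participation may end (section 14). It might cover a dose change, but not a rise in mood.

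**4. How many people the mismatch could cover.** Section 10 assigns 40 TBI patients and 40 controls to active stimulation. The share *f* on stable psychotropics is not given. Assuming *f* = 10%, 25% or 40% in the TBI group:
- active TBI patients: 40 × *f* = 4, 10 or 16;
- all TBI patients: 80 × *f* = 8, 20 or 32.

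The documents give neither a hypomania rate nor a rate of detection, so no expected number of cases follows.

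**5. Why a fixed rise in score is a poor trigger.** On a 10-point scale nobody who starts above 10 − 4 = 6 can rise by 4. If baseline scores had mean 5 and SD 2 (an assumption), the share starting above 6 would be 1 − Φ((6 − 5)/2) = 1 − 0.69 = 0.31. A rule that needs such a rise on both mood and energy would be out of reach for between 0.31 (baselines perfectly correlated) and 1 − 0.69² = 0.52 (independent). Those missed would include patients who start out elevated.

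**The case against.** The best defence is that the contradiction is one loose sentence and that patients are otherwise well watched. The two-month rule keeps out anyone who has recently started or changed a drug. The principal investigator, who has neuropsychiatry clinic experience (section 2), helps to give the stimulation. Adverse events are collected. The safety board reviews data quarterly and includes the director of an electroconvulsive therapy service. Psychiatric emergency care is 5 to 10 minutes' walk away (section 22). Mental health history and medication lists may be obtained. For a rare event, relying on clinical judgement is a legitimate choice, and raised mood is the effect that Aim 2 hopes for.

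Much of this stands. The stable-dose rule is a real partial guard and may be defensible, and a case could well be noticed. But it is not the guard that section 16 states, and none of the backstops mentions raised mood or hypomania.

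Three stronger readings are tempting and not supported.
- A reader might take "Safeguard exclusions that the study will have in place are enumerated above" as a claim that the medication exclusion is on the list. That sentence closes a separate discussion of brain injury and seizure risk and does not refer to hypomania or medication.
- A reader might infer that antidepressants are shown to raise the risk. Section 16 gives no denominator, its cases come from studies of depressed patients, and this trial selects on cognitive symptoms.
- A reader might infer that cases are likely or would be missed. No rate is given for either.

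**Conclusion.** The point holds as a contradiction about a safety measure, together with an absent response rule. Exclusion of psychotropic users is stated in section 16, contradicted by inclusion criterion 7 and missing from the Exclusion Criteria; for healthy controls the position is unclear. No written rule acts on a rise in mood or energy. Both statements rest on the text alone and can be made with confidence.

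The size is uncertain. The figure of 4 to 16 active TBI patients depends wholly on the assumed share of 10% to 40%, and the number of active controls affected is unknown. That the absence of a trigger needs remedy is a judgement: it is reasonable because section 16 relies on these ratings as a precaution and because the protocol already has a parallel rule for suicidal thoughts. The point should be corrected. It does not show the trial to be unsafe, and it does not touch the primary cognitive analysis.

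**What to change.** 1. **Make the sections agree.** Either correct section 16 to say that TBI patients on stable doses are admitted under the two-month rule, and report mood adverse events by medication use; or add the exclusion to the Exclusion Criteria. State which rule applies to healthy controls. The first option costs a sentence and a tabulation; the second narrows the recruitment pool.
2. **Ask about past mania or bipolar disorder** in the structured interview already held at screening. One of the two references cited for the hypomania cases (item 76) is titled as a bipolar II case; only the title is available here. Whether a positive answer should exclude is for the investigators.
3. **Extend the evaluation rule.** Add suspected hypomania to the rule in Depression Assessments that sends suicidal ideation to the principal investigator. Let it be prompted by a marked, sustained rise or by a near-ceiling level on the session mood and energy scales. The investigators should set the cut-off before use. It should not be a fixed 4-point rise, for the ceiling reason shown above.

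No visit or instrument is added. The downside is that some patients who respond well will be flagged, and the blinded principal investigator who evaluates them may guess their arm.
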